### Document History

Document	Version Date
Amendment 1	13 September 2022
Original protocol	27 May 2022

This amendment incorporates all revisions to date, including amendments made at the request of country health authorities and IRBs/ECs and any protocol administrative change letter(s).

## Protocol Amendment Summary of Changes Table

### Amendment 1 (13 September 2022):

**Overall Rationale for the Amendment:** This protocol was amended based on regulatory feedback to update the primary analysis and include an additional population of nonhospitalized symptomatic participants who are immunocompromised with a rebound in COVID-19.

Section # and Name	Description of Change	Brief Rationale	Substantial or Nonsubstantial
1.1 Synopsis 3.0 Objectives, Endpoints, and Estimands 9.1.1.1 Primary Estimand/Copri mary Estimands	Revised estimand to include patients who received non-study antiviral or monoclonal antibody therapy as not achieving the primary endpoint.	To address regulatory feedback recommending a more conservative approach and considering patients who received non-study antiviral or monoclonal antibody therapy as a failure in the primary analysis.	substantial
1.1 Synopsis 3.0 Objectives, Endpoints, and Estimands 9.1.1.1 Primary Estimand/Copri mary Estimands 9.3.2.1 Definitions of Endpoint(s) 9.3.2.2 Main Analytical Approach 9.5 Sample Size Determination	For the primary endpoint, changed the beginning of the sustained period from “the end of active treatment” to “Day 15”.	To address regulatory feedback recommending a standard follow-up period duration for all treatment groups for the primary endpoint.	substantial

Section # and Name	Description of Change	Brief Rationale	Substantial or Nonsubstantial
9.3.2.1 Definition of Endpoint(s)	Revised sustained definition for the primary endpoint NP swab SARS-CoV-2 RNA level from “not $\geq 2.5 \log_{10}$ copies/mL” to “not $\geq 2.0 \log_{10}$ copies/mL” at any study visit (through Day 44) following the first study visit where the participant’s NP swab SARS-CoV-2 RNA <LLOQ.	To address regulatory feedback recommending modification to the definition of sustained.	substantial
9.3.2.3 Supplementary Analysis/Analyses	Revised supplementary analysis for the primary endpoint to exclude data after the date of nonstudy antiviral or monoclonal antibody start for participants who received non-study antiviral or monoclonal antibody therapy.	To address regulatory feedback by designating this as a supplemental analysis instead of primary analysis.	substantial
1.1 Synopsis 2.1 Study Rationale 4.1 Overall Design 4.2 Scientific Rationale for Study Design	Added an additional population of participants to the study who are immunocompromised with COVID-19 rebound within 14 days following completion of an initial 5-day nirmatrelvir/ritonavir treatment course.	To address regulatory feedback by adding this population to the study.	substantial
1.1 Synopsis 5.1 Inclusion Criteria 10.9.5 Inclusion Criteria for Additional Population With COVID-19 Rebound	Added Inclusion Criterion #5 that allows participants who are immunocompromised and have COVID-19 rebound to enroll in the study; and added Section 10.9.5 that further describes inclusion criteria for the additional population with COVID-19 rebound.	To address regulatory feedback pertaining to the importance of studying rebound as a separate group of immunocompromised patients previously treated with a 5-day course of PAXLOVID.	substantial
1.1 Synopsis 5.1 Inclusion Criteria	Revised Inclusion Criterion #2 to specify participants with COVID-19 rebound must have confirmed SARS-CoV-2 infection as specified in Appendix 9, Section 10.9.2 for the main study population or Appendix 9, Section 10.9.5 for the additional population with rebound.	To address regulatory feedback pertaining to the importance of studying rebound as a separate group of immunocompromised	substantial

Section # and Name	Description of Change	Brief Rationale	Substantial or Nonsubstantial
10.9.2 Confirm SARS-CoV-2 Infection Details for the Main Study Population 10.9.5 Inclusion Criteria for Additional Population With COVID-19 Rebound		patients previously treated with a 5-day course of PAXLOVID and establishing specific inclusion criteria for this group.	
Synopsis 1.1 4.1 Overall Design 6.3 Assignment to Study Intervention	Added that enrollment of participants considered immunocompromised based solely on receiving corticosteroids or TNF blockers in the additional population with rebound will not be capped or stratified.	To clarify enrollment of participants in the additional population with rebound.	substantial
6.9 Prior and Concomitant Therapy 10.9.7 Prior/Concomitant Therapy	Added prior therapy of a 5-day nirmatrelvir/ritonavir course for participants in the additional population with rebound is required and not prohibited.	To be consistent with eligibility criteria.	substantial
8.5 Pharmacokinetics	Clarified that 1 mL of blood is needed for measurement of nirmatrelvir and ritonavir.	To clarify total blood volume so that extra blood is not needlessly drawn.	substantial
10.8 Prohibited Concomitant Medications That May Result in DDI	Text describing Tables 4 and 5 was revised to clarify DDI table content. Tables were updated with information from the Fact Sheet for Healthcare Providers: Emergency Use Authorization for Paxlovid (August 2022).	Updates to the list of precautionary and prohibited medications.	substantial

Section # and Name	Description of Change	Brief Rationale	Substantial or Nonsubstantial
Cover page and 1.1 Synopsis	Added NCT number.	To incorporate changes from the 12 July 2022 PACL.	nonsubstantial
1.1 Synopsis	Revised the definition of enrolled to include those who complete informed consent/assent and screening.	To clarify that potential participants who are screened for the purpose of determining eligibility for the study, but do not participate in the study, are not considered enrolled. To incorporate changes from the 12 July 2022 PACL.	nonsubstantial
1.1 Synopsis 4.1 Overall Design	Added text for the timing of enrollment for the additional population with rebound.	To clarify enrollment of the population with rebound in relation to the main study population.	nonsubstantial
Synopsis 1.1 4.1 Overall Design	Removed autoimmune disorder treatment for sole reason why enrolled participants receive corticosteroids or TNF blockers, which are capped at approximately 25%.	To clarify that participants on corticosteroids or TNF blockers, who are capped at ~25%, is not restricted to only participants treated for autoimmune disorders.	nonsubstantial
1.1 Synopsis 5.2 Exclusion Criteria 6.1 Study Intervention(s) Administered 6.1.1 Administration 6.6 Dose Modification 7.1 Discontinuation	Updated units for eGFR as mL/min/1.73m  and units for CrCl as mL/min. in these sections.	Updated for consistency.	nonsubstantial

Section # and Name	Description of Change	Brief Rationale	Substantial or Nonsubstantial
of Study Intervention			
1.1 Synopsis 9.1.1.1 Primary Estimand/Copri mary Estimands 9.3.2.1 Definition of Endpoint(s) 9.3.2.2 Main Analytical Approach	Clarified data will be analyzed separately for the main study population and the additional population with rebound.	To clarify data analysis.	nonsubstantial
1.1 Synopsis 4.1 Overall Design 9.5 Sample Size Determination	Added that sample size of participants with COVID-19 rebound would be up to 50, and accordingly specified that total sample size of study is up to 200 participants.	To specify maximum sample size of the additional population with rebound and maximum total sample size of study.	nonsubstantial
1.3 Schedule of Activities	
Added note for vital status check that secondary contacts may be used.
 
To be consistent with revisions to Inclusion Criterion #2, updated the note for a positive SARS-CoV-2 test obtained within 5 days for the main study population or 24 hours for the population with rebound prior to randomization.
 
Updated the note for the rapid antigen testing to clarify that postbaseline tests will be performed by an HCP.
 
Added cross-reference to Section 8.1.4 for telehealth activities and removed 'telemedicine' from Serious and nonserious AE monitoring notes since telehealth and telemedicine are synonymous.
	
Updated for consistency with Section 8.1.1.3.
 
To be consistent with Inclusion Criterion #2 and to clarify that postbaseline rapid antigen testing should be performed by an HCP as opposed to self-testing.
 
Updated for consistency with Section 8.1.4.
	nonsubstantial

Section # and Name	Description of Change	Brief Rationale	Substantiation
1.3 Schedule of Activities  CCI [Redacted] [Redacted]	CCI [Redacted]	[Redacted]	Nonsubstantial  [Redacted]
2.2 Background	Added information on rebound in COVID-19.	To provide clinical relevance on the addition of the population with rebound to this study.	nonsubstantial
4.1 Overall Design 9.0 Statistical Considerations 9.5 Sample Size Determination	Defined timing of analyses, described primary and follow-up analyses, and stated that the additional population with rebound will be analyzed separately from the main study population.	To clarify data analysis.	nonsubstantial
5.3.2 Other Restrictions	Included exception for participants who have an oncology disease.	To avoid excluding participants who are immunocompromised with an oncology disease who are often participating in oncology clinical trials from the study population. To incorporate changes from the 12 July 2022 PACL.	nonsubstantial
6.1.1 Administration	Updated timing of dose administration.	To align with dosing administration in other C467 protocols.	nonsubstantial

Section # and Name	Description of Change	Brief Rationale	Substantial or Nonsubstantial
6.3 Assignment to Study Intervention	Added stratification text for participants in the main study population who are considered immunocompromised solely based on corticosteroids or TNF blocker use.	Updated for consistency.	nonsubstantial
6.9 Prior and Concomitant Therapy	Described ritonavir is an inhibitor of CYP3A4 and provided guidance accordingly.	To provide clinical guidance for participants who take concomitant medications metabolized by CYP3A4.	nonsubstantial
8.1.1.1 Medical History	Added that risk factors for the participant developing severe COVID-19 illness will be recorded.	To clarify medical history.	nonsubstantial
8.1.1.3 Secondary Contacts	Added that secondary contacts may be used to determine if a participant is lost to follow-up or vital status check.	To clarify utility of collecting secondary contact information.	nonsubstantial
8.4.1 Time Period and Frequency for Collecting AE and SAE Information 8.4.1.1 Reporting SAEs to Pfizer Safety 8.4.5.1 Exposure During Pregnancy 8.4.5.2 Exposure During Breastfeeding	Updated CT SAE Report Form and the EDP Supplemental Form to PSSA and added minor edits for clarification.	To align with Pfizer's new platform for submission of SAEs to the Drug Safety Unit.	nonsubstantial

Section # and Name	Description of Change	Brief Rationale	Substantial or Nonsubstantial
8.4.5.3 Occupational Exposure 8.4.10 Medication En-ors 10.3.3 Recording/Reporting and Follow-Up of AEs and/or SAEs During the Active Collection Period 10.3.4 Reporting of SAEs			
CCI [Redacted]	[Redacted]	[Redacted]	[Redacted]
9.2 Analysis Sets	Clarified that analysis sets will be applied for the main study population and the population with rebound.	To clarify analysis sets defined in the protocol will be applied to both populations.	nonsubstantial
10.2 Appendix 2: Clinical Laboratory Assessments	Separated urea and creatinine .	To clarify they are 2 separate laboratory assessments. To incorporate changes from the 12 July 2022 PAEL.	nonsubstantial
10.4.2. Female Participant	Separated the paragraphs for WOCBP and WONCBP.	For clarification	nonsubstantial

Section # and Name	Description of Change	Brief Rationale	Substantial or Nonsubstantial
Reproductive Inclusion Criteria			
Section 10.9.4 Immunocompromised Criteria Details	Clarified length of time for corticosteroid use prior to study entry.	To clarify corticosteroid use requirements.	nonsubstantial
Throughout the protocol	General editorial changes.	To correct grammatical errors, to maintain consistency, and/or to increase clarity.	nonsubstantial

## 1. PROTOCOL SUMMARY

### 1.1. Synopsis

#### Protocol Title:

An Interventional Efficacy And Safety, Phase 2, Randomized, Double-Blind, 3-Arm Study To Investigate Nirmatrelvir/Ritonavir in Nonhospitalized Participants at Least 12 Years Of Age With Symptomatic COVID-19 Who Are Immunocompromised

#### Brief Title:

A Study to Learn About the Study Medicine Called Nirmatrelvir/Ritonavir in People at Least 12 Years of Age With COVID-19 Who Are Immunocompromised

#### Regulatory Agency Identification Number(s):

US IND Number:	153517
EudraCT/CTIS Number:	2022-001362-35
ClinicalTrials.gov ID:	NCT05438602
Pediatric Investigational Plan Number:	NA
Protocol Number:	C4671034
Phase:	2

#### Rationale:

Patients with COVID-19 who are immunocompromised are at increased risk of progressing to severe illness due to prolonged infection, limited contribution by the immune system in clearing the infection, and increased potential for viral resistance. Emergence of variants that are resistant to available treatment also puts the wider population at risk. Patients who are immunocompromised may benefit from extended treatment durations. The purpose of the study is to evaluate the efficacy and safety of nirmatrelvir/ritonavir (5, 10, and 15-day dosing durations) for the treatment of COVID-19 in nonhospitalized symptomatic participants  $\geq 12$  years of age and weigh  $\geq 40$  kg who are immunocompromised (main study population).

In addition, this study will also evaluate the efficacy and safety of a second treatment course of nirmatrelvir/ritonavir (5-, 10-, or 15-days) in an additional population of nonhospitalized symptomatic participants who are immunocompromised with a rebound in COVID-19 within 14 days following completion of an initial 5-day treatment course of nirmatrelvir/ritonavir (population with rebound).

## Objectives, Endpoints, and Estimands:

Objectives	Endpoints	Estimands
Primary:	Primary:	Primary:

 
To describe the effect of nirmatrelvir/ritonavir on viral RNA levels in NP swabs over time for the treatment of COVID-19 in nonhospitalized symptomatic participants <math>\geq 12</math> years of age with COVID-19 who are immunocompromised.
 
	
 
Proportion of participants with sustained NP swab SARS-CoV-2 RNA <math>< \text{LLOQ}</math> (defined as <math>< 2.0 \log_{10}</math> copies/mL) from Day 15 through Day 44.
 
	
 
The proportion of participants with sustained NP swab SARS-CoV-2 RNA <math>< \text{LLOQ}</math> (defined as <math>< 2.0 \log_{10}</math> copies/mL) from Day 15 through Day 44 in nonhospitalized, symptomatic patients <math>\geq 12</math> years of age with COVID-19 who are immunocompromised. This will be estimated without regard to study treatment discontinuation and considering participants receiving non-study antiviral or monoclonal antibody therapy post-baseline for the treatment of COVID-19 as not achieving sustained NP swab SARS-CoV-2 RNA <math>< \text{LLOQ}</math>.
 

Secondary:	Secondary:	Secondary:

 
To describe the effect of nirmatrelvir/ritonavir treatment duration on the rate of sustained virologic clearance in nonhospitalized symptomatic participants <math>\geq 12</math> years of age with COVID-19 who are immunocompromised.
 
	
 
Time to first NP swab SARS-CoV-2 RNA <math>< \text{LLOQ}</math> (<math>< 2.0 \log_{10}</math> copies/mL) for participants with NP swab SARS-CoV-2 RNA <math>\geq \text{LLOQ}</math> at baseline.
 
Time to sustained NP swab SARS-CoV-2 RNA <math>< \text{LLOQ}</math> (<math>< 2.0 \log_{10}</math> copies/mL) through Day 44 for participants with NP swab SARS-CoV-2 RNA <math>\geq \text{LLOQ}</math> at baseline.
 
	
 
Not applicable.
 


 
To describe the effect of nirmatrelvir/ritonavir on viral clearance for the treatment of COVID-19 in nonhospitalized symptomatic participants <math>\geq 12</math> years of age with COVID-19 who are immunocompromised.
 
	
 
Proportion of participants with SARS-CoV-2 RNA <math>< \text{LLOQ}</math> in plasma over time.
 
Proportion of participants with SARS-CoV-2 RNA level in NP swabs <math>< 2.0 \log_{10}</math> copies/mL at each study visit through Day 44.
 
Change from baseline in SARS-CoV-2 RNA level in NP swabs and in plasma over time.
 
Rebound in SARS-CoV-2 RNA level in NP swabs at follow up (ie, any study visit after end of treatment through Day 44) that is defined as a half (<math>0.5 \log_{10}</math> copies/mL) increase or greater in SARS-CoV-2 RNA level relative to end of treatment SARS-CoV-2 RNA level based on treatment regimen, with a follow-up viral RNA level <math>\geq 2.5 \log_{10}</math> copies/mL.
 
	
 
Not applicable.
 

 
To describe the safety and tolerability of nirmatrelvir/ritonavir
 
	
 
Incidence of TEAEs.
 
	
 
Not applicable.
 

Objectives	Endpoints	Estimands
for the treatment of COVID-19 in nonhospitalized symptomatic participants $\geq 12$ years of age with COVID-19 who are immunocompromised.	
 
Incidence of SAEs and AEs leading to discontinuations.
 
	

 
To describe the effect of nirmatrelvir/ritonavir on hospitalization and all-cause mortality in nonhospitalized symptomatic participants <math>\geq 12</math> years of age with COVID-19 who are immunocompromised.
 
	
 
Proportion of participants with COVID-19-related hospitalization >24 hours, or death from any cause through Day 28.
 
Proportion of participants with death (all cause) through Week 24.
 
	
 
Not applicable.
 


 
To describe COVID-19 related healthcare resource utilization in nonhospitalized symptomatic participants <math>\geq 12</math> years of age with COVID-19 who are immunocompromised and treated with nirmatrelvir/ritonavir.
 
	
 
Proportion of participants with COVID-19-related hospitalization of any duration.
 
Proportion of participants with COVID-19-related ICU admission of any duration.
 
Proportion of participants requiring invasive mechanical ventilation or ECMO.
 
Number of days in hospital and ICU stay in participants with COVID-19-related hospitalization.
 
Number of COVID-19-related medical visits through Day 44 and through Week 24.
 
	
 
Not applicable.
 

 
To evaluate nirmatrelvir/ritonavir for the duration and severity of signs and symptoms in nonhospitalized symptomatic participants <math>\geq 12</math> years of age with COVID-19 who are immunocompromised.
 
	
 
Duration of each targeted COVID-19 signs/symptoms.
 
Proportion of participants with severe signs/symptoms attributed to COVID-19 through Day 44.
 
	
 
Not applicable.
 

 
To determine the PK of nirmatrelvir/ritonavir in nonhospitalized symptomatic participants <math>\geq 12</math> years of age with COVID-19 who are immunocompromised.
 
	
 
Nirmatrelvir and ritonavir PK in plasma and whole blood (if feasible).
 
	
 
Not applicable.
 

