##### 9.1.1.2. Secondary Estimands

Not Applicable.

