### 9.5. Sample Size Determination

Up to approximately 200 participants will be enrolled in this study.

The study will randomize approximately 150 participants in a 1:1:1 randomization ratio, resulting in approximately 50 participants in each treatment arm (main study population). In addition, the study will also enroll up to 50 additional nonhospitalized symptomatic participants (in a 1:1:1 randomization ratio) who are immunocompromised with a rebound in COVID-19 within 14 days following completion of an initial 5-day treatment course of nirmatrelvir/ritonavir (population with rebound).

Analyses will be conducted after the main study population is fully enrolled and have completed the Day 44 visit regardless of the number of randomized participants in the population with rebound. There will be 2 analysis time points for reporting the results of this study. The primary analysis will be performed after all participants in the main study population have completed the Day 44 visit. The follow-up analysis will be performed after all participants in the main study population have completed the Week 24 visit. In addition, both analyses (primary and follow-up) will include separate results for the main study population and the additional population with rebound.

As no formal hypothesis testing will be performed for this study, no power calculation was carried out to assess the number of participants required for each treatment arm. For the main study population, the goal of the primary analysis is to estimate the treatment effect for each duration of nirmatrelvir/ritonavir. The smaller numbers of participants in these groups will be reflected in the precision of the estimate of the primary endpoint. Table 2 displays which effect sizes would be excluded based on the expected width of the confidence interval around the estimate of the proportion of participants with sustained NP swab SARS-CoV-2 RNA <LLOQ (defined as <2.0 log10 copies/mL) from Day 15 through Day 44 with a sample size of 50.

When the proportion of participants with sustained NP swab SARS-CoV-2 RNA <LLOQ from Day 15 through Day 44 ranges from 0.1 to 0.5, Table 2 displays the precision (width of the confidence interval) for the respective proportion to be estimated with a sample size of 50. That is, the width of the 95% CI does not exceed 14%.

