5.2.3. Analyses for Time-to-Event Endpoints

For time-to-event endpoints (eg, time to first NP swab SARS-CoV-2 RNA<LLOQ [<2.0 log_{10} copies/mL] for participants with NP swab SARS-CoV-2 RNA ≥LLOQ at baseline), Kaplan-Meier analysis where tabular summaries of the Kaplan-Meier curves providing the median and quartiles, will be provided for each treatment group. In addition, the Kaplan-Meier curves will be presented graphically.

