6.1.1. Main Analysis

The primary descriptive analysis will summarize, separately for the main study population and the population with rebound, the number and proportion of participants with sustained NP swab SARS-CoV-2 RNA <LLOQ (defined as <2.0 log₁₀ copies/mL) from Day 15 through Day 44 for each treatment arm in the Evaluable Analysis Set and FAS. Participants DMB02-GSOP-RF02 7.0 *Statistical Analysis Plan Template* 31-Jan-2022

> PFIZER CONFIDENTIAL TMF Doc ID: 98.03 Page 16 of 32

receiving non-study antiviral or monoclonal antibody therapy post-baseline (between randomization and Day 44 visit) for the treatment of COVID-19 will be considered as not achieving sustained NP swab SARS-CoV-2 RNA <LLOQ in the primary analysis.

As viral load measurements from NP swabs are taken on Days 15, 21, 28, 35, and 44 during the time interval from Day 15 to Day 44, all of the measurements that are non-missing must be <LLOQ (including undetectable), and the Day 15, Day 44, and no more than one of the Day 21, 28, and 35 measurements can be missing in order for the event to be considered sustained.

In addition, 95% CIs for the proportion of participants with sustained NP swab SARS-CoV-2 RNA <LLOQ from Day 15 through Day 44 for each treatment arm will be calculated using binomial distribution normal approximation. The difference in proportions for the primary endpoint and associated 95% CI will be calculated for each pairwise comparison of the treatment arms.

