6.2.1.1. Main Analysis

Time (days) to first NP swab SARS-CoV-2 RNA<LLOQ (<2.0 log₁₀ copies/mL) will be evaluated for participants with NP swab SARS-CoV-2 RNA \geq LLOQ at baseline. The first day of NP swab SARS-CoV-2 RNA<LLOQ will be considered the First Event Date. Time

DMB02-GSOP-RF02 7.0 Statistical Analysis Plan Template 31-Jan-2022 PFIZER CONFIDENTIAL TMF Doc ID: 98.03 Page 17 of 32 (days) to first NP swab SARS-CoV-2 RNA<LLOQ will be calculated as (First Event Date) – (First Dose Date) +1.

There are limitations to the timing of the first event date as NP viral RNA is generally only captured at in-person scheduled visits during the study.

The Day 44 visit day is the last possible day the NP swab SARS-CoV-2 RNA<LLOQ can be achieved.

For a participant that either completes the Day 44 visit of the study or discontinues from the study before the Day 44 visit without NP swab SARS-CoV-2 RNA<LLOQ (censored), censoring date will be at the last date on which NP swab SARS-CoV-2 RNA is assessed, and time will be calculated as (Censoring Date) – (First Dose Date) +1 or the Day 44 visit whichever occurs first.

Time to NP swab SARS-CoV-2 RNA<LLOQ will be summarized graphically using Kaplan-Meier plots for each of the treatment groups in main study population.

6.2.2. Time to sustained NP swab SARS-CoV-2 RNA <LLOQ (<2.0 log10 copies/mL) through Day 44 for participants with NP swab SARS-CoV-2 RNA ≥LLOQ at baseline

Time (days) to sustained NP swab SARS-CoV-2 RNA<LLOQ (<2.0 log₁₀ copies/mL) will be evaluated. Sustained is defined as NP swab SARS-CoV-2 RNA level not \geq 2.0 log₁₀ copies/mL at any study visit (through Day 44) following the first study visit where the participant's NP swab SARS-CoV-2 RNA <LLOQ.

Let *t* represent the number of days between 5 and 35 inclusive for which there is a protocol-specified measurement of SARS-CoV-2 RNA level on Day *t*.

Then a sustained event will correspond to the first possible value of *t* to satisfy the following criteria:

- a) The Day 44 SARS-CoV-2 RNA level is <LLOQ
- b) The Day t SARS-CoV-2 RNA level is <LLOQ
- c) All available (non-missing) protocol-specified SARS-CoV-2 RNA measurements between Day *t* and Day 44 are <LLOQ
- d) No more than one of the protocol-specified SARS-CoV-2 RNA measurements between Day *t* and Day 44 are missing.

There are limitations to the timing of the first event date as NP viral RNA is generally only captured at in-person scheduled visits during the study.

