The Day 35 visit is the last possible day the sustained NP swab SARS-CoV-2 RNA<LLOQ can be achieved.

DMB02-GSOP-RF02 7.0 Statistical Analysis Plan Template 31-Jan-2022 PFIZER CONFIDENTIAL TMF Doc ID: 98.03 Page 18 of 32 The time to the sustained event is defined as:

- For a participant with sustained event at Day *t*, the First Event Date is the date of the Day *t* measurement, and time to event will be calculated as (First Event Date) (First Dose Date) +1.
- For a participant for which no possible value of *t* ≤ the 35 visit satisfies the criteria for a sustained event (censored), censoring date will be the date of the last available protocol-specified SARS-CoV-2 RNA measurement other than Day 44, and time will be calculated as (Censoring Date) (First Dose Date) +1.

Time to sustained NP swab SARS-CoV-2 RNA<LLOQ will be summarized graphically using Kaplan-Meier plots for each of the treatment groups in main study population.

6.2.3. Proportion of participants with SARS-CoV-2 RNA <LLOQ in plasma over time.

• The proportion of participants with SARS-CoV-2 RNA <LLOQ as measured in plasma will be summarized at each study visit through week 24 for each treatment arm. In addition, 95% CIs for the proportion of participants with SARS-CoV-2 RNA <LLOQ in plasma at each study visit will be calculated for each treatment arm.

6.2.4. Proportion of participants with SARS-CoV-2 RNA level in NP swabs <2.0 log₁₀ copies/mL at each study visit

The proportion of participants with SARS-CoV-2 RNA < 2.0 log₁₀ copies/mL as measured by NP swab will be summarized at each study visit through Week 24 for each treatment arm. In addition, 95% CIs for the proportion of participants with SARS-CoV-2 RNA <2.0 log₁₀ copies/mL as measured by NP swabs at each study visit will be calculated for each treatment arm.

6.2.5. Change from baseline in SARSCoV-2 RNA level in NP swabs and in plasma over time.

Descriptive statistics by treatment group for the change from baseline to each study visit (Day 5, 10, 15, 21, 28, 35, 44) will be provided. Participants are excluded from the analysis for reasons of Not Detected, Zero or Missing baseline and/or post-baseline viral load results.

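### The time-to-clearance endpoints under the treatment-duration objective get per-arm Kaplan-Meier summaries only, with no between-duration estimate or interval

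*Protocol*

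**What the plan says.** Protocol Section 3 and the Synopsis state the first secondary objective as "To describe the effect of nirmatrelvir/ritonavir treatment duration on the rate of sustained virologic clearance". It is the only objective that names treatment duration, the randomized factor. Its endpoints are time to first and time to sustained RNA below 2.0 log10 copies/mL, in participants at or above that limit at baseline.

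The planned analysis of these endpoints is per arm throughout:

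- SAP 5.2.3, for time-to-event endpoints in general: "Kaplan-Meier analysis where tabular summaries of the Kaplan-Meier curves providing the median and quartiles, will be provided for each treatment group", plus plotted curves.
- SAP 6.2.1.1, first clearance: "Time to NP swab SARS-CoV-2 RNA<LLOQ will be summarized graphically using Kaplan-Meier plots for each of the treatment groups in main study population".
- SAP 6.2.2, sustained clearance: "Time to sustained NP swab SARS-CoV-2 RNA<LLOQ will be summarized graphically using Kaplan-Meier plots for each of the treatment groups in main study population".
- SAP Appendix 1 lists only Kaplan-Meier curves as the analysis model for both.

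Protocol 9.1.1.2 gives secondary estimands as "Not Applicable", and SAP 2.2.2 agrees. No hazard ratio, difference in clearance probability, difference in medians or restricted-mean difference is named.

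For the primary endpoint the plan goes further. SAP 6.1.1 states: "The difference in proportions for the primary endpoint and associated 95% CI will be calculated for each pairwise comparison of the treatment arms". SAP 6.2.4 adds, for each arm, the proportion below the limit at each visit with a 95% CI, but no difference between arms.

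**The concern.** All three arms receive active drug and differ only in its duration. An effect of duration on clearance is therefore a contrast between arms, and the objective that asks for it has no such contrast in its own analysis. A reader who wants to know how much sooner virus clears with 10 or 15 days than with 5 would have to compare curves and quantiles without a measure of uncertainty. If someone computes a contrast later, its form will have been chosen after unblinding.

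The median, the most quotable of the planned summaries, is also coarse here. Swabs are scheduled on seven post-baseline days through Day 44, an event is dated at the visit that shows it, and SAP 6.2.1.1 itself acknowledges this limit on timing.

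**Working it through.** **Plan's own figure.** There is none for these endpoints. Protocol 9.5 says "no power calculation was carried out to assess the number of participants required for each treatment arm". Table 2 concerns a single-arm proportion for the primary endpoint: its 0.139 at p = 0.5 is 1.96 × √(0.5 × 0.5 / 50), and it does not bear on time to clearance.

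**Inputs from the documents.** Visits on Days 5, 10, 15, 21, 28, 35 and 44; visit windows of 1 to 3 days either side (Schedule of Activities); about 50 per arm; event time from actual dates, as event date minus first dose date plus 1 (SAP 6.2.1.1).

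**Inputs assumed.** The documents give no clearance rates. The illustration takes cumulative clearance at the seven visits as:

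| Day | 5 | 10 | 15 | 21 | 28 | 35 | 44 |
|---|---|---|---|---|---|---|---|
| Arm A | 15% | 51% | 65% | 76% | 85% | 90% | 93% |
| Arm B | 15% | 66% | 83% | 91% | 95% | 97% | 98% |

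**Step 1: quantiles.** Both true medians are Day 10. The 75th percentile is Day 21 in A and Day 15 in B.

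**Step 2: restricted mean to Day 44.** This is the sum of interval length × proportion not yet cleared.

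- A: 5 + 5(0.85) + 5(0.49) + 6(0.35) + 7(0.24) + 7(0.15) + 9(0.10) = 17.43 days.
- B: 5 + 5(0.85) + 5(0.34) + 6(0.17) + 7(0.09) + 7(0.05) + 9(0.03) = 13.22 days.
- Difference: 4.21 days.

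**Step 3: precision.** The variance of the restricted time is 445.17 − 17.43² = 141.4 in A and 242.22 − 13.22² = 67.5 in B. SE = √((141.4 + 67.5)/n), ignoring dropout.

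| Contributors per arm | SE | 95% CI (days) |
|---|---|---|
| 50 | 2.04 | 0.2 to 8.2 |
| 45 | 2.15 | about 0.0 to 8.4 |
| 40 | 2.28 | −0.3 to 8.7 |

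The lower rows matter because both endpoints are restricted to participants with baseline RNA at or above the limit, so fewer than 50 per arm may contribute.

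**Step 4: how often the planned quantiles hide the difference.** 20,000 simulated trials, 50 per arm. The last column spreads visits uniformly within the protocol windows, which is an assumption.

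| | Nominal visit days | Actual dates within windows |
|---|---|---|
| Medians identical | 61% | about 30% |
| Medians within 1 day | – | about 60% |
| Both quartiles and the median identical | about 7% | under 1% |

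On nominal days the third quartiles differ in 91% of trials.

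**Step 5: sensitivity to the assumed rates.** With exponential clearance, latent medians of 6 to 14 days in the slower arm and jittered visits (2,000 trials each), the two medians fall on the same nominal visit in these shares of trials:

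| Hazard ratio | Same nominal visit |
|---|---|
| 1.0 (no difference) | 47–76% |
| 1.25 | 39–75% |
| 1.5 | 24–60% |
| 2.0 | 9–22% |

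At a hazard ratio of 1.5, exact ties by actual date occur in 6–25%. For a modest effect, shared-visit medians are therefore almost as common as with no effect.

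**The case against.** Four points count on the other side.

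*The trial is descriptive, with no testing.* True, and the absence of tests is not the defect. The primary analysis shows that the plan treats pairwise differences with intervals as compatible with a descriptive design.

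*A reader might infer that the trial estimates no duration effect at all.* The documents do not support that. The primary analysis contrasts durations on sustained clearance from Day 15 through Day 44, which is close to the objective's wording, and SAP 6.2.4 gives visit-wise proportions with per-arm intervals. But the primary outcome is binary. Clearing at Day 5 or at Day 15 scores the same, and someone still at or above the limit on Day 15 who clears by Day 21 is a failure. It cannot say how much sooner virus clears, and its main analysis is not restricted to participants with quantifiable baseline RNA.

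*A reader might infer that the planned output would often show no difference.* That does not follow either. The SAP plans quartiles and curves as well as medians, and Step 4 shows that all three quantiles rarely coincide. The 61% tie rate applies only to nominal days, whereas the SAP uses actual dates. It also reflects an illustration in which one arm sits at 51% on Day 10, just past the median threshold.

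*The restricted mean is one choice among several.* This stands in part. A difference in clearance probability at named visits would also fill the gap, with a 95% CI of roughly ±0.18 to ±0.20 at 50 per arm, ignoring censoring. The horizon also needs care: Day 35 and Day 44 visits may fall up to 3 days early, and participants without the event are censored at their last eligible swab, so follow-up on actual dates can end before the horizon.

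**Conclusion.** The point holds for the two time-to-clearance endpoints of the first secondary objective: the SAP specifies no between-duration estimate and no interval for them. That conclusion comes from the text and needs no assumption. The clustering of medians is a secondary point, and its frequency rests on clearance rates that the documents do not supply.

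The illustrated 4.2-day difference is likewise assumed. What it shows is the likely precision: about plus or minus 4 days at 40 to 50 contributors per arm. The interval of 0.2 to 8.2 days should not be read as showing that such an effect would be distinguished from zero. It needs all 50 per arm to have quantifiable baseline RNA, and at 45 the lower limit is already about zero. An imprecise contrast is still better reported with its interval than judged by eye.

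**What to change.** In SAP 5.2.3, 6.2.1, 6.2.2 and Appendix 1, add for 10 versus 5 days and 15 versus 5 days the difference in restricted mean time to clearance with its 95% CI, among participants with baseline RNA at or above the limit.

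- Horizon: Day 44 for first clearance and Day 35 for sustained clearance, matching the last possible event visits in SAP 6.2.1.1 and 6.2.2.
- Timing: use nominal visit days, or set the horizon no later than the last follow-up common to the arms, so that a visit made early within its window does not leave the estimate undefined.
- Reporting: place it beside the Kaplan-Meier output, labelled descriptive, without a test. Stratifying by the randomization factor is optional.

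The cost is SAP wording and one table from data already collected. The downside is two more unadjusted and fairly wide intervals per endpoint.
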